4.2 Reporting Adverse Events and Intercurrent Illnesses

In the event of an SAE, whether associated with study drug or not, the investigator will notify Clinical Pharmacovigilance within 24 hours after the site becomes aware of the SAE by entering the SAE data into the electronic data capture (EDC) system. SAEs that occur before the site having access to the RAVE[®] system, or if RAVE is not operable, should be documented on the SAE non-CRF forms and emailed (preferred route) or faxed to Clinical Pharmacovigilance within 24 hours after the site becomes aware of the SAE.

Email: [contact] FAX to: [contact]

For safety concerns, contact the Neuroscience Safety Team at:

Neuroscience Safety Team [name] [name]

Office: [contact]

Email: [contact]

For any subject safety concerns, please contact the physician listed below:

Primary Therapeutic Area Medical Director EMERGENCY MEDICAL CONTACT:

PhD AbbVie

[name]

Contact Information:

Office:	
Mobile:	
Mobile 2:	
Email:	

In emergency situations involving study subjects when the primary Therapeutic Area Medical Director is not available by phone, please contact the 24-hour AbbVie Medical Escalation Hotline where your call will be re-directed to a designated backup AbbVie Therapeutic Area Medical Director:

[contact]

The sponsor will be responsible for Suspected Unexpected Serious Adverse Reactions (SUSAR) reporting for the Investigational Medicinal Product (IMP) in accordance with Directive 2001/20/EC.

COVID-19 Pandemic-Related Acceptable Protocol Modifications

Supplemental study case report forms should be completed in the event of COVID-19-related missed/virtual visits, study drug interruptions or discontinuations, or adverse events (including capture of specific signs/symptoms of infection and testing results).

COVID-19 infections should be captured as adverse events. If the event meets the criteria for a serious adverse event (SAE), then follow the SAE reporting directions per the protocol and above. The following COVID-19-related supplemental eCRFs should be completed (for both serious and nonserious events):

- COVID-19 Supplemental Signs/Symptoms
- COVID-19 Status Form

If a subject has a confirmed or suspected COVID-19 infection and study drug was interrupted, the investigator should contact the sponsor emergency medical contact listed above before reintroducing study drug.

5 COUNTRY-SPECIFIC REQUIREMENTS

5.1 Sample Retention Requirements

AbbVie (or people or companies working with AbbVie) will store the biomarker samples and data in a secure storage space with adequate measures to protect confidentiality. The samples may be retained while research on elezanumab (or drugs of this class) or MS and related conditions continues, but for no longer than 20 years after study completion or according to local requirements.

5.2 SUSAR Reporting

AbbVie will be responsible for Suspected Unexpected Serious Adverse Reactions (SUSAR) reporting for the Investigational Medicinal Product (IMP) in accordance with global and local guidelines and Appendix A of the Investigator Brochure will serve as the Reference Safety Information (RSI). The RSI in effect at the start of a DSUR reporting period serves as the RSI during the reporting period. For followup reports, the RSI in place at the time of occurrence of the 'suspected' Serious Adverse Reaction will be used to assess expectedness.

5.3 Treatment After End of Study

For active subjects randomized to elezanumab or placebo, subjects will continue on study treatment throughout the study for a period of up to 52 weeks or until premature discontinuation of study drug. At the subject's last study visit, the investigator will discuss the appropriate subsequent treatment with the subject. AbbVie will not provide drug or any other therapy once the subject's participation is concluded.

APPENDIX A. STUDY-SPECIFIC ABBREVIATIONS AND TERMS

Abbreviation	Definition
9НРТ	9-hole peg test
ADA	Antidrug antibody
ADLs	Activities of daily living
AE	Adverse event
AESI	Adverse event of special interest
aPTT	Activated partial thromboplastin time
ALT	Alanine aminotransferase
AST	Aspartate aminotransferase
BAC	Brief Assessment of Cognition
BMI	Body mass index
BUN	Blood urea nitrogen
ClinRo	Clinician reported outcome
COVID-19	Coronavirus Disease - 2019
СРК	Creatine phosphokinase
CRF	Case report form
CS	Clinically significant
C-SSRS	Columbia-Suicide Severity Rating Scale
D/C	Discontinuation
DNA	Deoxyribonucleic acid
ECG	Electrocardiogram
eCOA	Electronic Clinical Outcome Assessments
eCRF	Electronic case report form
EDC	Electronic data capture
EDSS	Expanded Disability Status Scale
EDSS +	Expanded Disability Status Scale Plus (EDSS +)
HBsAg	Hepatitis B surface antigen
HCV	Hepatitis C virus
HIV	Human immunodeficiency virus
IEC	Independent ethics committee
IMP	Investigational medical product
INR	International normalized ratio

IRB	Institutional review board
IRT	Interactive response technology
IV	Intravenous
LCVA	Low Contrast Visual Acuity
LLN	Lower limit of normal
MedDRA	Medical Dictionary for Regulatory Activities
MFIS-5	Modified Fatigue Impact Scale
MRI	Magnetic resonance imaging
MS	Multiple sclerosis
MSIOA	Multiple Sclerosis Individualized Outcome Assessment
MSIS-29	Multiple Sclerosis Impact Scale
nAb	Elezanumab neutralizing antibody
NCS	Not clinically significant
PCS	Potentially clinically significant
РК	Pharmacokinetic(s)
PRO	Patient reported outcome
PT	Preferred term
RBC	Red blood cells
RNA	Ribonucleic acid
RSI	Reference safety information
SAE	Serious adverse event
SDMT	Symbol Digit Modalities Test
sEMG	Surface electromyography
SOC	System organ class
SUSAR	Suspected unexpected serious adverse reaction
TA MD	Therapeutic Area Medical Doctor
T25FW	Timed 25 Foot Walk
ULN	Upper limit of normal
WBC	White blood cell

APPENDIX B. CRITERIA FOR POTENTIALLY CLINICALLY SIGNIFICANT (PCS) VALUES FOR ELEZANUMAB STUDIES

CTCAE v4.0 Term*	PCS Value/ Grade	PCS Value	Grade 1	Grade 2	Grade 3	Grade 4
Hematology				•	•	
Activated partial thromboplastin time prolonged (aPTT)	1	> ULN	> ULN – 1.5 × ULN	> 1.5 – 2.5 × ULN	> 2.5 × ULN; hemorrhage	
Hemoglobin decreased	2	< 10.0 g/dL	< LLN – 10.0 g/dL	< 9 – 8.0 g/dL	< 8.0 g/dL	Life-threatening
		< 6.2 mmol/L	< LLN – 6.2 mmol/L	< 6.2 – 4.9 mmol/L	< 4.9 mmol/L	consequences; urgent intervention
		< 100 g/L	< LLN – 100 g/L	< 100 – 80 g/L	< 80 g/L; transfusion	indicated
Hemoglobin increased	3	> 4 gm/dL above ULN	Increase in > 0 – 2 gm/dL above ULN or above baseline if baseline is above ULN	Increase in > 2 – 4 gm/dL above ULN or above baseline if baseline is above ULN	Increase in > 4 gm/dL above ULN or above baseline if baseline is above ULN	
INR increased	1	> ULN	> 1 - 1.5 × ULN	> 1.5 – 2.5 × ULN	> 2.5 × ULN	
			> 1 – 1.5 times above baseline if on anticoagulation	> 1.5 – 2.5 times above baseline if on anticoagulation	> 2.5 times above baseline if on anticoagulation	
Leukocytosis (WBC increased)	3	> 100,000/mm ³			> 100,000/mm ³	Clinical manifestations of leucostasis; urgent intervention indicated
Lymphocyte count	3	< 500/mm ³	< LLN – 800/mm ³	< 800 – 500/mm ³	< 500 - 200/mm ³	< 200/mm ³
decreased		< 0.5 × 10 ⁹ /L	< LLN - 0.8 × 10 ⁹ /L	< 0.8 - 0.5 × 10 ⁹ /L	< 0.5 - 0.2 × 10 ⁹ /L	< 0.2 × 10 ⁹ /L
Lymphocyte count increased	3	> 20,000/mm ³		> 4000 – 20,000/mm ³	> 20,000/mm ³	

	PCS Value/					
CTCAE v4.0 Term*	Grade	PCS Value	Grade 1	Grade 2	Grade 3	Grade 4
Hematology (continued)						
Neutrophil count decreased	3	< 1000/mm ³	< LLN – 1500/mm ³	< 1500 - 1000/mm ³	< 1000 – 500/mm ³	< 500/mm³
		< 1.0 × 10 ⁹ /L	< LLN - 1.5 × 10 ⁹ /L	< 1.5 – 1.0 × 10 ⁹ /L	< 1.0 – 0.5 × 10 ⁹ /L	< 0.5 × 10 ⁹ /L
Platelet count decreased	2	< 75,000/mm ³	< LLN – 75,000/mm ³	< 75,000 – 50,000/mm³	< 50,000 – 25,000/mm ³	< 25,000/mm ³
		< 75.0 × 10 ⁹ /L	< LLN - 75.0 × 10 ⁹ /L	< 75.0 - 50.0 × 10 ⁹ /L	< 50.0 - 25.0 × 10 ⁹ /L	< 25.0 × 10 ⁹ /L
White blood cell decreased	3	< 2000/mm ³	< LLN – 3000/mm ³	< 3000 - 2000/mm ³	< 2000 – 1000/mm ³	< 1000/mm ³
		< 2.0 × 10 ⁹ /L	< LLN - 3.0 × 10 ⁹ /L	< 3.0 – 2.0 × 10 ⁹ /L	< 2.0 – 1.0 × 10 ⁹ /L	< 1.0 × 10 ⁹ /L
Chemistry						
Blood bilirubin increased	2	> 1.5 × ULN	> ULN - 1.5 × ULN	> 1.5 - 3.0 × ULN	> 3.0 - 10.0 × ULN	> 10.0 × ULN
Cholesterol high	4	> 500 mg/dL	> ULN – 300 mg/dL	> 300 – 400 mg/dL	> 400 – 500 mg/dL	> 500 mg/dL
		> 12.92 mmol/L	> ULN – 7.75 mmol/L	> 7.75 – 10.34 mmol/L	> 10.34 – 12.92 mmol/L	> 12.92 mmol/L
Creatinine increased	2	> 1.5 × ULN	> 1 – 1.5 × baseline	> 1.5 – 3.0 × baseline	> 3.0 baseline	> 6.0 × ULN
			> ULN – 1.5 × ULN	> 1.5 – 3.0 × ULN	> 3.0 - 6.0 × ULN	
GGT increased	2	> 2.5 × ULN	> ULN – 2.5 × ULN	> 2.5 – 5.0 × ULN	> 5.0 - 20.0 × ULN	> 20.0 × ULN

	PCS Value/					
CTCAE v4.0 Term*	Grade	PCS Value	Grade 1	Grade 2	Grade 3	Grade 4
Chemistry (continued)		-			-	-
			Co	rrected Serum Calcium	of:	
Hypercalcemia	3	> 12.5 mg/dL	> ULN – 11.5 mg/dL	> 11.5 – 12.5 mg/dL	> 12.5 – 13.5 mg/dL	> 13.5 mg/dL
		> 3.1 mmol/L	> ULN – 2.9 mmol/L	> 2.9 – 3.1 mmol/L	> 3.1 – 3.4 mmol/L	> 3.4 mmol/L
				Ionized Calcium		
		> 1.6 mmol/L	> ULN – 1.5 mmol/L	> 1.5 – 1.6 mmol/L; symptomatic	> 1.6 – 1.8 mmol/L; hospitalization indicated	> 1.8 mmol/L; life- threatening consequences
			Fasting Glu	icose Value		
Hyperglycemia	3	> 250 mg/dL	> ULN – 160 mg/dL	> 160 – 250 mg/dL	> 250 – 500 mg/dL	> 500 mg/dL
		> 13.9 mmol/L	> ULN – 8.9 mmol/L	> 8.9 – 13.9 mmol/L	> 13.9 – 27.8 mmol/L; hospitalization indicated	> 27.8 mmol/L; life- threatening consequences
Hyperkalemia	3	> 6.0 mmol/L	> ULN – 5.5 mmol/L	> 5.5 – 6.0 mmol/L	> 6.0 – 7.0 mmol/L; hospitalization indicated	> 7.0 mmol/L; life- threatening consequences
Hypermagnesemia	3	> 3.0 mg/dL	> ULN – 3.0 mg/dL		> 3.0 – 8.0 mg/dL	> 8.0 mg/dL
		> 1.23 mmol/L	> ULN – 1.23 mmol/L		> 1.23 – 3.30 mmol/L	> 3.30 mmol/L; life- threatening consequences
Hypernatremia	3	> 155 mmol/L	> ULN – 150 mmol/L	> 150 – 155 mmol/L	> 155 – 160 mmol/L; hospitalization indicated	> 160 mmol/L; life- threatening consequences

CTCAE v4.0 Term*	PCS Value/ Grade	PCS Value	Grade 1	Grade 2	Grade 3	Grade 4
Chemistry (continued)						
Hypertriglyceridemia	3	> 500 mg/dL	150 – 300 mg/dL	> 300 – 500 mg/dL	> 500 – 1000 mg/dL	> 1000 mg/dL
		> 5.7 mmol/L	1.71 – 3.42 mmol/L	> 3.42 – 5.7 mmol/L	> 5.7 – 11.4 mmol/L	> 11.4 mmol/L; life- threatening consequences
Hyperuricemia (Uric Acid	4	> 10 mg/dL	> ULN – 10 mg/dL		> ULN – 10 mg/dL	> 10 mg/dL
Increased)		> 0.59 mmol/L	(0.59 mmol/L) without physiologic consequences		(0.59 mmol/L) with physiologic consequences	> 0.59 mmol/L; life- threatening consequences
Hypoalbuminemia	3	< 2 g/dL	< LLN – 3 g/dL	< 3 – 2 g/dL	< 2 g/dL	Life-threatening
		< 20 g/L	< LLN – 30 g/L	< 30 – 20 g/L	< 20 g/L	consequences; urgent intervention indicated
			C	orrected Serum Calciu	m	
Hypocalcemia	3	< 7.0 mg/dL	< LLN – 8.0 mg/dL	< 8.0 – 7.0 mg/dL	< 7.0 – 6.0 mg/dL	< 6.0 mg/dL
		< 1.75 mmol/L	< LLN – 2.0 mmol/L	< 2.0 – 1.75 mmol/L	< 1.75 – 1.5 mmol/L	< 1.5 mmol/L
				Ionized Calcium		
		< 0.9 mmol/L	< LLN – 1.0 mmol/L	< 1.0 – 0.9 mmol/L; symptomatic	< 0.9 – 0.8 mmol/L; hospitalization indicated	< 0.8 mmol/L; life- threatening consequences
Hypoglycemia	3	< 40 mg/dL	< LLN – 55 mg/dL	< 55 – 40 mg/dL	< 40 – 30 mg/dL	< 30 mg/dL
		< 2.2 mmol/L	< LLN – 3.0 mmol/L	< 3.0 – 2.2 mmol/L	< 2.2 – 1.7 mmol/L	< 1.7 mmol/L; life- threatening consequences; seizures

CTCAE v4.0 Term*	PCS Value/ Grade	PCS Value	Grade 1	Grade 2	Grade 3	Grade 4
Chemistry (continued)						
Hypokalemia	3	< 3.0 mmol/L	< LLN – 3.0 mmol/L	< LLN – 3.0 mmol/L; symptomatic; intervention indicated	< 3.0 – 2.5 mmol/L; hospitalization indicated	< 2.5 mmol/L; life- threatening consequences
Hypomagnesemia	3	< 0.9 mg/dL	< LLN – 1.2 mg/dL	< 1.2 – 0.9 mg/dL	< 0.9 – 0.7 mg/dL	< 0.7 mg/dL
		< 0.4 mmol/L	< LLN – 0.5 mmol/L	< 0.5 – 0.4 mmol/L	< 0.4 – 0.3 mmol/L	< 0.3 mmol/L; life- threatening consequences
Hyponatremia	3	< 130 mmol/L	< LLN – 130 mmol/L		< 130 – 120 mmol/L	< 120 mmol/L; life- threatening consequences
Hypophosphatemia	3	< 2.0 mg/dL	< LLN – 2.5 mg/dL	< 2.5 – 2.0 mg/dL	< 2.0 – 1.0 mg/dL	< 1.0 mg/dL
		< 0.6 mmol/L	< LLN – 0.8 mmol/L	< 0.8 – 0.6 mmol/L	< 0.6 – 0.3 mmol/L	< 0.3 mmol/L; life- threatening consequences
Enzymes						
Alanine aminotransferase (ALT) increased	2	> 3 × ULN	> ULN - 3.0 × ULN	> 3.0 – 5.0 × ULN	> 5.0 – 20.0 × ULN	> 20.0 × ULN
Alkaline phosphatase increased	2	> 2.5 × ULN	> ULN – 2.5 × ULN	> 2.5 – 5.0 × ULN	> 5.0 – 20.0 × ULN	> 20.0 × ULN
Aspartate aminotransferase (AST) increased	2	> 3 × ULN	> ULN - 3.0 × ULN	> 3.0 – 5.0 × ULN	> 5.0 – 20.0 × ULN	> 20.0 × ULN
CPK increased	3	> 5 × ULN	> ULN – 2.5 × ULN	> 2.5 × ULN – 5 × ULN	> 5 × ULN – 10 × ULN	> 10 × ULN

Adapted from the Common Terminology Criteria for Adverse Events (CTCAE) Version 4.0 Published: May 28, 2009 (v4.03: June 14, 2010)

* Common Terminology Criteria for Adverse Events (CTCAE) Version 4.0 Published: May 28, 2009 (v4.03: June 14, 2010).

Criteria for Potentially Clinically Significant (PCS) Vital Sign Values for Elezanumab Studies

Vital Signs Variables	Criterion	Potentially Clinically Significant (PCS) Value
Systolic blood pressure (mm Hg)	Low	≤ 90 mm Hg and decrease ≥ 20 mm Hg from Baseline
	High	≥ 180 mm Hg and increase ≥ 20 mm Hg from Baseline
Diastolic blood pressure (mm Hg)	Low	\leq 50 mm Hg and decrease \geq 15 mm Hg from Baseline
	High	≥ 105 mm Hg and increase ≥ 15 mm Hg from Baseline
Heart rate (bpm)	Low	\leq 50 bpm and decrease \geq 15 bpm from Baseline
	High	\geq 120 bpm and increase \geq 15 bpm from Baseline
Temperature	High	\geq 38.3°C and \geq 1.1°C above baseline value

APPENDIX C. MS RELAPSE QUESTIONNAIRE

- 1. Adverse Event Serial number:
- 2. Provide Individual Symptom(s) (New or increasing MS symptoms from baseline):

- 3. Diagnosis made by:
 Symptoms
 MRI
 Both MRI and Symptoms
- 4. Change in Neurological Examination from baseline consistent with MS relapse?
 □ Yes □ No
- 5. Have the symptoms lasted at least 24 hours?
 See Yes
 No
- 6. Have the symptoms occurred in the absence of fever?

 Yes
 No
- 7. Has it been more than 30 days since the prior relapse? \Box Yes \Box No
- 8. Is there an alternative etiology for symptoms beside MS Relapse?

 Yes
 No
- 9. Narrative for course of event for symptom(s) recorded above. Include details of neurological findings, treatment, and response as applicable. Treatment medications should also be entered into the Concomitant Medication eCRF.

- 10. Date Review Completed by MS Relapse Adjudication Committee (RAC)
- 11. RAC panel confirmed MS Relapse?
 □ Yes □ No

APPENDIX D. CRITERIA FOR MONITORING ELEZANUMAB INFUSION REACTIONS

Infusion Reactions

Potential infusion reactions have been observed in the Phase 1b Study M14-173, though no reactions were consistent with anaphylaxis or required medical intervention. Subjects will be closely monitored for treatment-related adverse events, especially infusion reactions during all study drug infusions.

Treatment of Infusion Reactions

Appropriate medical therapy including epinephrine, corticosteroids, intravenous antihistamines, bronchodilators, and oxygen should be available for use in the treatment of such reactions. Subjects should be carefully observed until the complete resolution of all signs and symptoms. In the event of a suspected infusion/anaphylactic reaction, in addition to the standard AE and Concomitant Medication eCRFs, a supplemental AESI eCRF should also be completed by site staff.

Reflexive Testing Following Infusion Reactions

If any infusion or suspected allergic-type reaction is observed, a blood draw is required within 2 hours after the first sign of a reaction for the following laboratory tests:

• C3a, C5 complement functional assay, IgE level, and serum tryptase level.

Anaphylactic Infusion Reactions

In the event of an anaphylactic reaction, blood samples will be drawn after the onset of the reaction for: histamine and tryptase. A blood sample for serum anti-drug antibody (ADA) assessment will also be collected within 2 hours of onset of anaphylactic reaction along with 1 hour blood samples for C3a, C5 complement functional assay, IgE level, and serum tryptase level. Separate instructions for the collection, handling, storage and shipping of these lab samples will be provided in the Covance Laboratory Manual.

Moderate Infusion Reactions

In situations where an infusion reaction occurs before the end of infusion and leads to clinically significant vital signs, skin or persistent gastrointestinal symptoms, treatment should be immediately interrupted. Once symptoms have resolved, re-initiating treatment is allowed with an infusion over 180 minutes. If infusion reactions persist despite the use of extended infusion times and medication, sites should contact the Therapeutic Area Medical Director regarding continued subject eligibility.

In the event of a suspected infusion/anaphylactic reaction, in addition to the standard AE eCRF, a supplemental AESI eCRF should also be completed by the site.

3.0 Introduction

This statistical analysis plan (SAP) describes the statistical analyses to be completed by the AbbVie Clinical Statistics Department for the elezanumab Phase 2a Study M18-918.

Pharmacokinetics/pharmacodynamics, pharmacogenetic, and selected biomarkers will be analyzed separately and are not included in this SAP.

Unless noted otherwise, all analyses will be performed using SAS version 9.4 or later (SAS Institute Inc., Cary, NC 27513) under the UNIX operating system.

The SAP will not be updated in case of future administrative or minor amendments to the protocol, unless the changes have an impact on the analysis of study data.

4.0 Study Background

4.1 Objective

The objective of this study is to evaluate the safety and efficacy of elezanumab in subjects with relapsing forms of multiple sclerosis (RMS).

4.2 Study Design

[figure not shown]
4.2.1 Study Design and Design Diagram

This is a 52-week, Phase 2a, proof-of concept, randomized, double-blinded, parallel-group, placebo-controlled multicenter study to evaluate the safety and efficacy of 2 doses of elezanumab in adult subjects with relapsing forms of MS who have established disability.

This study will include an approximate 30-day Screening period. The Treatment Period will include fourteen (14) visits from Baseline (Week 0) every four weeks through Week 52. Doses will be administered via intravenous (IV) infusion at Week 0 (Baseline) and every 4 weeks thereafter through Week 48 for a total of 13 doses. The follow-up period includes two visits that will occur at Weeks 64 and 76.

The total study duration is up to 80 weeks. The schematic of the study is shown in [Figure 1](#). Further details regarding study procedures are located in the Operations Manual.

Figure 1. Study Schematic

- * During the Follow-up Period and after the Week 76 visit, female subjects of childbearing potential are to complete monthly home urine pregnancy tests for 39 weeks (5 half-lives) after last dose; and for all subjects adverse events will be collected, whether solicited or spontaneously reported by the subject throughout the study and for a period of 39 weeks after the last dose of study drug.

4.2.2 Variables used for Stratification at Randomization

Randomization will be stratified by diagnosis of MS form [relapsing remitting MS (RRMS) vs. relapsing secondary-progressive MS (rSPMS)], and presence of background MS immunotherapy (Yes vs. No).

The stratification variables used in the analyses will be based on the MS type from the MS Disease History eCRF and MS immunotherapy on the first dose date from the Concomitant Medications eCRF.

4.3 Endpoint

4.3.1 Primary Efficacy Endpoint

The primary efficacy endpoint is the Overall Response Score (ORS) at Week 52.

ORS is a composite score derived from 4 components:

- Expanded Disability Status Scale (EDSS)
- Timed 25-Foot Walk (T25FW)
- 9-Hole Peg Test in the dominant hand (9HPT-D)
- 9HPT in the non-dominant hand (9HPT-ND)

The EDSS + is a composite derived from the EDSS, T25FW, 9HPT-D and 9HPT-ND where responder status is defined as a clinical meaningful improvement on one or more of these endpoints. Hereafter, the EDSS, T25FW, 9HPT-D and 9HPT-ND will also be referred to as "components of the EDSS +" or "components of the ORS."

The ORS is scored with a range from -4 to +4 at each assessment for all post-baseline visits. Scores for each component are assessed relative to their baseline value: -1 if there is clinically significant worsening, 0 if the change does not meet the clinically significant threshold criteria, or +1 if there is clinically significant improvement. The scores for all components are summed at each assessment. If any of the 4 components of the ORS are missing within a visit window, then the ORS will be considered missing for that visit.

The clinically significant change thresholds for EDSS, T25FW and 9HPT are provided in the following table.

ORS Components	Score of ORS Components at Post-Baseline Visits		
	-1 (Clinically Significant Worsening)	0 (No Clinically Significant Change)	1 (Clinically Significant Improvement)
EDSS change from baseline	≥ 1 if baseline EDSS ≤ 5.5 ; ≥ 0.5 if baseline EDSS ≥ 6.0	-0.5, 0 or 0.5 if baseline EDSS ≤ 5.5 ; 0 if baseline EDSS ≥ 6.0	≤ -1 if baseline EDSS ≤ 5.5 ; ≤ -0.5 if baseline EDSS ≥ 6.0
T25FW change from baseline	$\geq 20\%$	$> -20\%$ and $< 20\%$	$\leq -20\%$
9HPT-D change from baseline	$\geq 20\%$	$> -20\%$ and $< 20\%$	$\leq -20\%$
9HPT-ND change from baseline	$\geq 20\%$	$> -20\%$ and $< 20\%$	$\leq -20\%$

4.3.2 Secondary Efficacy Endpoints

The secondary efficacy endpoints include:

- Disability improvement responder status (Yes or No) on the EDSS+ at Week 52
- ORS at Weeks 12, 24, and 36

4.3.3 Exploratory Efficacy Endpoints

The exploratory efficacy endpoints include:

- Disability improvement response rate on the EDSS, T25FW, 9HPT-D, and 9HPT-ND at Weeks 12, 24, 36, and 52, and the EDSS + at Weeks 12, 24, and 36.
- Change from Baseline on the T25FW, 9HPT-D, 9HPT-ND at Weeks 12, 24, 36, and 52
- Disability progression response rate on the Expanded Disability Status Scale Plus (EDSS +) (T25FW, 9-Hole Peg test [9HPT, either hand], EDSS) and for each EDSS + component

- 12- and 24-week confirmed disability improvement response rate on the EDSS + and for each EDSS + component
- Change from Baseline on the Multiple Sclerosis Impact Scale (MSIS-29) total score at Weeks 12, 24, 36, and 52
- Change from Baseline on the Modified Fatigue Impact Scale (MFIS) total score at Weeks 12, 24, 36, and 52
- Change from Baseline on cognition battery at Weeks 12, 24, 36, and 52:
 - Total score of the Symbol Digit Modalities Test (SDMT) – Oral Version
 - Total score and T-score of the Brief Assessment of Cognition Verbal Memory - Immediate Recall – BAC App Version
 - Total score and T-score of the Brief Assessment of Cognition Tower of London – BAC App Version
- Change from Baseline on the Low Contrast Visual Acuity (LCVA) assessments at Weeks 12, 24, 36, and 52
- Change from Baseline in select plasma biomarkers for monitoring target binding, neuroprotection and/or neurorestoration at Weeks 12, 24, 36, and 52
- Change from Baseline on the MS Individualized Outcome Assessment (MSIOA) scale overall symptom score and most bothersome symptom score at Weeks 24, and 52
- Change from Week 0 in average daily step count and other activity measures (as described in Section 9.4.3) via home actigraphy with wearable biosensor initiated at Weeks 24, 36, and 52
- Summary of variables from brain MRI at Baseline, Weeks 24 and 52
 - Presence of active T1 Gadolinium (GAD)-enhancing lesions
 - Presence of active new and enlarging T2 hyperintense lesions
 - Cumulative number of total T1 GAD-enhancing, lesions
 - Cumulative number of total T2 hyperintense lesions
 - Cumulative number of post-baseline T1 GAD-enhancing lesions
 - Cumulative number of post-baseline new and enlarging T2 lesions
 - Number of T1 GAD-enhancing lesions at each visit
 - Change from Baseline in total volumes of T1 GAD-enhancing, lesions

- Change from Baseline in total volume of T2 hyperintense lesions
- Change from Baseline in whole brain, gray matter (GM), thalamus, white matter (WM) and normal appearing white matter (NAWM) volumes
- Change from Baseline in regional magnetization transfer ratio (MTR) parameters for whole brain, and NAWM, and MTR for T2 lesions
- Change from baseline in lesion MTR for T1 (GAD)-enhancing lesions and delta MTR
- Change from Baseline in diffusion tensor imaging (DTI) parameters (fractional anisotropy and Apparent Diffusion Coefficient (ADC)) for whole brain, NAWM and T2 hyperintense lesions
- Summary of variables from cervical spinal MRI at Weeks 24 and 52
 - Change from Baseline in cervical spinal cord area, volume and number of lesions
 - Change from Baseline in regional MTR for cervical spinal cord lesions
 - Change from baseline in DTI parameters (fractional anisotropy and ADC) for cervical spinal cord

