3.7 Exploratory Endpoints

- 1. Disability improvement response rate on the T25FW, 9HPT, either hand, and EDSS at Weeks 12, 24, 36, and 52, and the EDSS + at Weeks 12, 24, and 36.
- 2. Change from Baseline on the T25FW and 9HPT, either hand, at Weeks 12, 24, 36, and 52
- 3. Disability progression response rate on the EDSS+ (T25FW, 9HPT, either hand, EDSS) and for each EDSS + component
- 4. 12- and 24-week confirmed disability improvement response rate on the EDSS + (T25FW, 9HPT, either hand, EDSS) and for each EDSS + component
- 5. Change from Baseline on the MS Impact Scale (MSIS-29) version 2 at Weeks 12, 24, 36, and 52
- 6. Change from Baseline on the Modified Fatigue Impact Scale (MFIS) at Weeks 12, 24, 36, and 52
- 7. Change from Baseline on cognition battery at Weeks 12, 24, 36, and 52:
 - Symbol Digit Modalities Test (SDMT) Oral Version
 - Brief Assessment of Cognition Verbal Memory Immediate Recall BAC App Version

- Brief Assessment of Cognition Tower of London BAC App Version
- Change from Baseline on the Low Contrast Visual Acuity (LCVA) assessments at Weeks 12, 24, 36, and 52
- 9. Change from Baseline in plasma biomarkers at Weeks 12, 24, 36, and 52
- 10. Change from Baseline on the MS Individualized Outcome Assessment (Multiple Sclerosis Individualized Outcome Assessment [MSIOA]) scale at Weeks 24 and 52
- 11. Change from Baseline in one week average daily step count and other activity measures (via home actigraphy with wearable biosensor) initiated at Weeks 24, 36, and 52

MRI Endpoints

The following imaging tests will be conducted. Details will be provided in the Statistical Analysis Plan (SAP).

- Lesion counts and volumes
- Brain and spinal cord atrophy measures
- Magnetization transfer ratio (MTR)
- Diffusion tensor imaging (DTI)

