3.14 Actigraphy

A wearable sensor will be used (when allowed per local regulatory guidelines) to enable data capture on actigraphy (activity, rest cycles) and daily step count. If regulatory approval in a participating country has not been received by the manufacturer, actigraphy data monitoring will not be done in that country. The actigraphy assessment will use BioStamp nPoint, which is a wireless remote monitoring platform intended for use by healthcare professionals and researchers for the continuous collection of physiological data in healthcare and home settings. BioStamp nPoint is designed to capture objective, real-world data from study subjects participating in clinical or academic studies and may be used wherever collection of relevant data is needed. BioStamp nPoint centers on body-worn BioStamp Sensors that can be worn for up to 24 hours at a time.

When BioStamp nPoint is used in the home or outside of the clinic ("Remote") setting, study subjects interact with the system through a Mobile Phone Application called the "Link App." The recharging and data transmission hub ("Link Hub") is used to recharge the sensors and synchronize data from the Sensors. The system is also capable of surface electromyography (sEMG) and monitoring limb and body movements during daily living and sleep. Training will be provided to site staff with instructions for subject use. Refer to Section 2 for the required administration times.

COVID-19 Pandemic-Related Acceptable Protocol Modifications

In the event this may not be performed due to study modifications related to the COVID-19 pandemic, actigraphy data will be captured at the next earliest feasible visit.

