9.4.9 Actigraphy

Actigraphy was collected for 7 days starting at the visits at Week 0 (Baseline), 24, 36, and 52. The actigraphy parameters of movement including average gait cadence, moving duration, walking duration, number of steps and resting duration will be analyzed.

Moving duration, walking duration, number of steps, and resting duration will be normalized for the number of hours per day the subject is wearing the device, i.e., divided by the (device wear time duration [in seconds] \div 3600).

The analysis of change from Week 0 for each of the moving duration, walking duration, number of steps, and resting duration will be based on the average hourly value for that visit, i.e., the Week X value will be the sum of the daily average hourly values for that parameter divided by the number of days the subject wore a sensor within a window. The analysis of change from Week 0 for average gait cadence will be based on the average daily value of gait cadence for that visit, i.e., the Week X value will be the sum of the daily mean gait cadence values divided by the number of days the subject wore a sensor within a window. The pooled standard deviation, effect size, and 95% confidence interval of the effect size will also be noted.

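### Average daily step count is named as an exploratory endpoint, but SAP 9.4.9 analyses only steps per hour of device wear, so the named measure gets no result

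*SAP*

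**What the plan says.** Protocol 3.7 (item 11) names the endpoint as "Change from Baseline in one week average daily step count and other activity measures", from home actigraphy. SAP 4.3.3 carries it over as "Change from Week 0 in average daily step count and other activity measures" and refers to Section 9.4.3 for the other measures. Section 9.4.3 covers the T25FW; actigraphy is in 9.4.9.

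SAP 9.4.9 states that "number of steps, and resting duration will be normalized for the number of hours per day the subject is wearing the device"; the time spent moving and the time spent walking are handled in the same way. For these parameters, "the Week X value will be the sum of the daily average hourly values for that parameter divided by the number of days" on which a sensor was worn. Average gait cadence is the one parameter not divided by wear time, and it measures pace, not a count. No analysis of steps per day is specified.

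On wear, Protocol 4.1 requires use on 7 consecutive days at each of four time points. The Operations Manual (Protocol Appendix F, Section 3.14) describes "body-worn BioStamp Sensors that can be worn for up to 24 hours at a time" and says the system is able to monitor movement in daily life and in sleep. Neither document states required hours per day, a rule on night wear, or a minimum wear time for a day to count.

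**The concern.** There are two linked problems.

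First, the endpoint and its analysis are different quantities. Steps per day and steps per hour of wear agree in relative change only if wear hours stay constant. The reference to other activity measures covers moving, walking and resting time. It does not turn the one explicitly named measure into a rate.

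Second, the denominator is total wear time. Hours worn asleep add to the denominator and almost nothing to the numerator. A subject who walks the same amount but wears the sensor for longer or shorter at night will show a change in the analysed value. Each worn day also has equal weight, however short the wear.

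At stake is how one exploratory result can be read. A change, or lack of change, in steps per wear-hour could be reported as a finding on daily steps when it is not one.

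**Working it through.** The documents give no actigraphy figure to reproduce, so the check applies the SAP 9.4.9 formula to assumed inputs.

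**From the documents**
- Daily value = steps ÷ (wear seconds ÷ 3600), that is, steps per wear-hour (SAP 9.4.9).
- Visit value = sum of daily values ÷ number of days worn (SAP 9.4.9).
- Maximum continuous wear: 24 hours (Operations Manual 3.14).

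**Assumed, not in the documents**
- Wear between 14 and 24 hours a day.
- 5,000 steps a day, with no steps in the added or removed night hours.

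**Step 1. Same walking, different wear.** If daily steps S are constant and wear goes from h0 to h1 hours, the analysed value goes from S/h0 to S/h1. The relative change is h0/h1 − 1, and S cancels. The change in daily steps is 0% in every row.

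| Wear at Week 0 → later (h) | Steps per wear-hour | Change in analysed value |
|---|---|---|
| 14 → 16 | 357.1 → 312.5 | −12.5% |
| 16 → 20 | 312.5 → 250.0 | −20.0% |
| 16 → 24 | 312.5 → 208.3 | −33.3% |
| 14 → 22 | 357.1 → 227.3 | −36.4% |
| 24 → 16 | 208.3 → 312.5 | +50.0% |
| 22 → 14 | 227.3 → 357.1 | +57.1% |

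The percentages are the same at 3,000 and 7,000 steps a day.

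**Step 2. A real change combined with a wear change.** If daily steps truly rise by 20%, the analysed change is 1.2 × h0/h1 − 1:
- 16 → 20 h: 1.2 × 16/20 − 1 = −4.0%
- 16 → 24 h: 1.2 × 16/24 − 1 = −20.0%
- 24 → 16 h: 1.2 × 24/16 − 1 = +80.0%

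**Step 3. Group level.** Suppose a share p of one arm moves from 16 to 24 h, the rest do not change, and starting rates are equal. The arm mean shifts by p × (16/24 − 1): −3.3% for p = 10%, −6.7% for 20% and −10.0% for 30%.

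**Step 4. The opposite case.** Suppose the 5,000 steps are spread evenly over 16 waking hours and the sensor is worn for only 8 of them. The recorded count is 5,000 × 8/16 = 2,500, or −50% in daily steps. The hourly rate is 2,500/8 = 312.5, which is unchanged. The raw count is therefore sensitive to missed daytime wear, and the hourly rate to night wear.

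**The case against.** The strongest reply is that dividing by wear time is a deliberate, prespecified answer to incomplete wear. Step 4 shows what it protects against. Partial days are foreseeable, because the Activity Schedule (Protocol Appendix D) has the equipment worn at the visit and for the 7 days after it. This stands: the hourly rate should stay, and replacing it with a raw count would exchange one weakness for another.

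A reader might infer from the Operations Manual that the sensors are meant for round-the-clock use, so that night wear did distort the results. The text does not support that. Twenty-four hours is an upper limit, and sleep monitoring is described as a capability. The sensors also need recharging, so some non-wear is expected at times that are not stated.

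A reader might also infer a biased comparison between arms. Subjects and site staff are blinded, and nothing in the documents suggests that wear would change differently by arm. Without that, wear changes mainly add noise.

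Rules on valid days may exist in the separate statistical programming plan (SAP 11.1 and 12.1) or in the training material, neither of which was available here. That could soften the point about the missing wear minimum. It would not remove the mismatch between SAP 4.3.3 and 9.4.9.

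**Conclusion.** The mismatch is established from the text alone: both documents name daily steps, and the SAP specifies only an hourly rate. The cross-reference error is also plain.

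The sensitivity to wear follows from the SAP's formula, but its size rests on assumed wear hours. For one subject with unchanged walking, a switch between 16 and 24 h moves the analysed value by −33% or +50%. If 10% to 30% of one arm lengthened wear in this way, the arm mean would move by about −3% to −10%. Whether any such shift occurred cannot be told from the documents.

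It would go too far to say that the trial could miss a walking effect because of this. Walking speed is tested directly by the T25FW, which is part of the primary endpoint and has its own analysis in SAP 9.4.3. Step count is exploratory in a Phase 2a study. The point is minor and leaves the primary and secondary conclusions untouched.

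**What to change.** 1. In SAP 9.4.9, add an analysis of change from Week 0 in average daily step count, over days that meet a prespecified minimum wear time. Keep the wear-normalised hourly rate beside it.
2. Summarise wear hours per day by arm and visit, so that the two results can be read together.
3. In SAP 4.3.3, change the cross-reference from 9.4.3 to 9.4.9.
4. Optionally, use waking wear hours as the denominator for the hourly rate, but only if the device output separates sleep from waking. SAP 9.4.9 lists resting duration, which is not the same as sleep.

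The cost is SAP wording and some programming; steps and wear time are already inputs to 9.4.9. The downside is that days below the minimum drop out of the daily-step analysis, and this loss may be informative if low wear goes with greater disability or fatigue. The number of days dropped should therefore be reported by arm. Protocol Appendix E reports that the planned efficacy analysis has already been done, so an analysis added now should be labelled as supplementary and added afterwards.
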